6.1. Primary Objective

The primary objective of this study is to test the hypothesis that dulaglutide (0.75 mg and 1.5 mg, pooled) given subcutaneously (SC) once a week for 26 weeks to children and adolescents with T2DM who have inadequate glycemic control, despite diet and exercise, with or without metformin and/or basal insulin is superior to placebo in the treatment of T2DM, as measured by baseline to Week 26 change in HbA1c.

6.2. Secondary Objectives

The secondary objectives of the study are to assess the efficacy, safety, PK and pharmacodynamics (PD) in patients.

The key secondary efficacy objectives are to compare the dulaglutide 0.75 mg and dulaglutide 1.5 mg arms (individually and pooled) to placebo with respect to the following parameters:

- Change in HbA1c between baseline and Week 26 (individual doses only)
- Change in fasting blood glucose (FBG) between baseline and Week 26
- Percentage of patients with HbA1c <7.0% at Week 26
- Change in body mass index (BMI) between baseline and Week 26

The other secondary efficacy objectives are to assess the 2 dulaglutide treatment groups (individually and pooled) with respect to the following parameters:

- Change in HbA1c between baseline and Week 52
- Change in FBG between baseline and Week 52
- Percentage of patients with HbA1c <7.0% at Week 52
- Change in BMI between baseline and Week 52

The secondary safety objectives are to compare the dulaglutide 0.75 mg and dulaglutide 1.5 mg arms (individually and pooled) to placebo with respect to the following parameters at 26 weeks, and to assess the following parameters in the dulaglutide 0.75 mg and dulaglutide 1.5 mg arms (individually and pooled) at Week 52:

- Glucose management-related safety assessed by the incidence of self-reported hypoglycemic events and the incidence of patients requiring rescue for severe, persistent hyperglycemia
- Pancreatic safety assessed by the incidence of cases of pancreatitis confirmed by adjudication and the effect on pancreatic enzymes
- Thyroid-related safety assessed by the incidence of cases of thyroid treatment-emergent adverse events (TEAEs) and effect on serum calcitonin
- Immune system-related safety, including the incidence of dulaglutide anti-drug antibodies (ADAs), and the incidence of allergic, hypersensitivity, and injection site reactions.

The secondary PK/PD objective is:

- Characterization of the PK of dulaglutide and the relationship between dulaglutide exposure and key safety and efficacy measures.

6.3. Exploratory Objectives

The exploratory objectives are to compare the dulaglutide 0.75 mg and dulaglutide 1.5 mg arms (individually and pooled) to placebo with respect to the following parameters at 26 weeks, and to assess the following parameters in the dulaglutide 0.75 mg and dulaglutide 1.5 mg arms (individually and pooled) at Week 52 (unless otherwise specified):

- Percentage of patients with HbA1c $\leq 6.5\%$ at Weeks 26 and 52
- Change in HbA1c between baseline and Week 13
- Percentage of patients having HbA1c $< 7.0\%$ without severe, documented symptomatic (< 70 mg/dL), or probable hypoglycemic episodes at Weeks 26 and 52
- Percentage of patients having HbA1c $\leq 6.5\%$ without severe, documented symptomatic (< 70 mg/dL), or probable hypoglycemic episodes at Weeks 26 and 52
- Change in weight between baseline and Weeks 26 and 52
- Change in hormone-related safety assessed by the effect on morning serum prolactin, insulin-like growth factor-1 (IGF-1), estradiol, testosterone (males only), luteinizing hormone (LH), and cortisol between baseline and Weeks 26 and 52
- Change in serum lipids between baseline and Weeks 26 and 52
- Change in Tanner staging between baseline and Weeks 26 and 52
- Change in BMI standard deviation score (SDS) between baseline and Weeks 26 and 52
- Change in height and height SDS between baseline and Weeks 26 and 52
- Change in waist circumference between baseline and Weeks 26 and 52
- Change in the EQ-5D-Y VAS score between baseline and Weeks 26 and 52
- Percentage of patients reporting each level of problem on each dimension of the EQ-5D-Y at baseline, weeks 26 and 52
- Assess the effect of dulaglutide on measures of insulin resistance, beta cell function, and serum adiponectin at Weeks 13 and 26
- Change in basal insulin dose from baseline to Week 26 and from baseline to Week 52

7. Investigational Plan

7.1. Summary of Study Design

Study H9X-MC-GBGC (GBGC) is a Phase 3, multicenter, randomized, double-blind, parallel-arm, placebo-controlled superiority trial with an open-label extension. Approximately 150 male and female children and adolescents (ages 10 to <18 years) with T2DM and inadequate glycemic control on diet and exercise alone or diet and exercise plus metformin and/or basal insulin will be enrolled. Randomization will be stratified by the patient's background therapy, and screening HbA1c. There will be a limitation on the number of patients with inadequate glycemic control managed by diet and exercise alone who have not previously received metformin so that these patients constitute no more than 25% of the total number of completers. The sponsor may place limitations on the patients enrolled depending on their demographics to meet regulatory expectations.

The main study has 4 periods: (1) a screening period lasting up to 4 weeks; (2) a double-blind treatment period lasting 26 weeks; (3) an open-label extension period lasting 26 weeks; and (4) a 30-day safety follow-up period. The end of trial is the date of the last visit or last scheduled procedure shown in the Study Schedule ([Attachment 1](#)) for the last patient.

One of the following measures will be offered to reduce pain associated with venipuncture: anesthetic creams, anesthetic patches, or high pressure anesthetic delivery system immediately before venipuncture.

Patients are discouraged from donating blood or blood products during the trial and for 30 days thereafter.

Figure [GBGC.1](#) illustrates the study design.

[figure not shown]

Figure GBGC.1. Illustration of study design for Clinical Protocol H9X-MC-GBGC.

Screening period: Patients may be rescreened twice for any reason. At the screening visit, during which patients may be in the non-fasted state, the parent or legal guardian will sign the informed consent form (ICF) and the patient will sign the assent form. If the patient has reached the age of majority per local country regulations, a separate assent document may not be required, as the patient is eligible to sign the ICF. The patients will then undergo assessments related to the inclusion and exclusion criteria.

Week -4: Screening Visit

At this visit, the following will be performed:

- A complete medical history will be taken along with full date of birth.
- Vital signs will be measured, along with height and weight, and BMI will be calculated.
- The patient's concomitant medications will be documented, including diabetes medications.
- Blood will be collected and sent to the central laboratory (see the Study Schedule, [Attachment 1](#)).
- Females of childbearing potential will have documentation of the date of their last menstrual period and a serum pregnancy test will be performed. A local urine pregnancy

test may be performed if pregnancy is suspected (see the Study Schedule, [Attachment 1](#)). If either test is positive, the patient will be excluded from the trial.

- Females of childbearing potential will undergo questioning about the use of effective contraception (see [Attachment 4](#)).
- For those patients who are not immediately excluded, both the patient and parent or legal guardian may be trained on how to use the dulaglutide single-dose pen (SDP) using the demonstration pen, which has no needle and contains no medication.

The patient and parent or legal guardian will be given an appointment to return to the clinic within 4 weeks (± 7 days), in the fasted state, for the randomization visit, assuming the patient meets all inclusion and no exclusion criteria at that time.

Double-blind treatment period: This treatment period will last for 26 weeks. With the exception of a telephone visit scheduled 1 week after randomization, study visits will occur approximately monthly: face-to-face visits in the clinic will occur at 1 month (Week 4), 3 months (Week 13), and 6 months (Week 26) and telephone visits will occur in between the face-to-face visits (Weeks 9, 18, and 22). Any phone visit may be converted to a face-to-face visit if deemed medically necessary by study personnel. Optional visits may occur between regularly scheduled visits if deemed medically necessary. If a patient misses a face-to-face visit, every effort must be made to reschedule the visit as soon as possible. If a patient misses a phone visit, the visit should be rescheduled as soon as possible. If the patient misses several visits, every effort must be made to get the patient to return to the clinic, even if it is only for the last visit. A parent or legal guardian should accompany the patient to each clinic visit—whether the parent/legal guardian must be present at each phone visit should be determined by the parent/legal guardian and study personnel.

At the randomization visit (Week 0), for those patients taking background diabetes medication, the metformin and basal insulin doses will be established. Generally, background diabetes medication should not be increased more than 15% during the double-blind period, though it may be decreased at any time if the patient experiences hypoglycemia (see Section [9.8](#); for the definition of hypoglycemia, see Section [10.4.1.2.1](#)).

During the entire trial, patients should perform self-monitoring of blood glucose (SMBG) in the fasted state and at 1 other time each day, as well as at any time they have symptoms suggestive of hypoglycemia. For each hypoglycemic episode, patients should record their blood glucose level (if available), associated symptoms, and treatment in the study diaries provided. For this study, a hypoglycemic episode should be noted as having occurred any time a patient feels that (s)he is experiencing a sign or symptom associated with hypoglycemia OR has a blood glucose level <70 mg/dL (<3.9 mmol/L), even if asymptomatic. The time and date of all SMBG readings must be recorded in the study diaries as well as the date and time of weekly study drug administration.

If pregnancy is suspected at any time in females of childbearing potential, a local urine pregnancy test will be performed and a serum pregnancy test will be sent to the central

laboratory. If the patient is pregnant, she must be permanently discontinued from study drug and the study.

Week 0: Randomization

At this visit, the patient will return to the clinic in the fasted state. The following will be performed:

- All inclusion and exclusion criteria must be reviewed to ensure that the patient qualifies for the trial.
- A physical examination by a physician will be performed which includes Tanner staging.
- Vital signs will be measured, along with height, weight, and waist circumference, and BMI will be calculated.
- Blood and urine will be collected for baseline laboratory tests and sent to the central laboratory.
 - A local urine pregnancy test must be performed for all females of childbearing potential prior to randomization. If positive, the patient will not be randomized.
- An electrocardiogram (ECG) will be performed.
- Concomitant medications will be documented.
- The baseline background diabetes medication dose (for those patients taking metformin and/or basal insulin) will be established. Generally, once this dose is established, it should not be increased more than 15% during the double-blind period, although it may be decreased at any time if the patient experiences hypoglycemia (see Section 9.8).
- Females of childbearing potential will have documentation of the date of their last menstrual period and will be questioned about the use of effective contraception (see [Attachment 4](#)).
- The patient will complete the EQ-5D-Y health outcomes questionnaires.
- The patient will receive:
 - Study diaries for the recording of glycemic and other information and instructions on how to fill them out.
 - A glucometer and supplies, as well as any training needed to use the glucometer.
 - Diet and exercise instruction for their T2DM.
 - Training for the patient and parent or legal guardian on how to use the SDP using the demonstration pen.
 - A supply of study drug (after the investigator uses the Interactive Web-Response System [IWRS] to get the study drug assignment).

At the conclusion of this visit, the patient, caregiver, or study personnel (whichever is deemed most appropriate by study personnel) will inject the patient with the first dose of study drug, noting the time and date of injection in the study diary. This day now becomes the patient's day of study drug administration.

The patient will be sent home with appointments for 1 telephone visit, which will occur in 1 week (Week 1) and for a clinic visit in 4 weeks (Week 4) in the non-fasted state.

Week 1: Telephone Visit (Visit Window up to ± 3 days)

At this visit, the following will be performed:

- The contents of the study diary for the previous week will be reviewed:
 - Self-monitoring of blood glucose results
 - Hypoglycemia events
 - Adverse event information
 - The date and time of all study drug injections
 - Any new concomitant medications or change in metformin or insulin dose
 - Females: The date of the last menstrual period

Week 4: Clinic Visit (Visit Window up to ± 7 days)

At this visit, the patient will return to the clinic in the non-fasted state. The following will be performed:

- A symptom-directed physical examination by a physician will be performed.
- Vital signs will be measured, along with height and weight.
- Concomitant medication information will be documented.
- If a female is of childbearing potential, the use of effective contraception will be discussed (see [Attachment 4](#)).
- Study diaries will be collected and the following reviewed:
 - Self-monitoring of blood glucose results
 - Hypoglycemia events
 - Adverse event information
 - The date and time of all study drug injections
 - Females: The date of the last menstrual period
- A local urine pregnancy test will be performed for all females of childbearing potential.
- The patient will receive:
 - Study diaries
 - Glucometer supplies
 - Diet and exercise instruction for their T2DM
 - Study drug. (At this visit, those patients who were assigned in a blinded fashion to 1.5 mg dulaglutide will be titrated from 0.75 mg/week to 1.5 mg/week. Therefore, prior to dispensing study drug to any patient, the physician will confirm via IWRS that the patient tolerated the previous 4 weeks of blinded study drug.)

The patient will be sent home with appointments for 1 telephone visit, which will occur in 5 weeks (Week 9) and for a clinic visit in 9 weeks (Week 13) in the fasted state.

Week 9: Telephone Visit (Visit Window up to ± 7 days)

At this visit, the following will be performed:

- Concomitant medication information will be documented
- If a female is of childbearing potential, the use of effective contraception will be discussed (see [Attachment 4](#)).
- The contents of the study diaries for the previous month will be reviewed:
 - Self-monitoring of blood glucose results
 - Hypoglycemia events
 - Adverse event information
 - The date and time of all study drug injections
 - Females: The date of the last menstrual period

Week 13: Clinic Visit (Visit Window up to ± 7 days)

At the half-way point in the double-blind portion of the clinical trial, the patient will return to the clinic in the fasted state. This visit must occur on the date of the patient's usual weekly injection of study drug, and before injection of study drug, as the patient will undergo collection of blood for a pre dose PK level at this visit, inject study drug and have a post dose PK level drawn. The following will be performed:

- Blood will be collected for a predose PK level, noting the exact date and time.*
- This will be followed by injection of study drug, noting the exact date and time.
- A symptom-directed physical exam by a physician will be performed.
- Vital signs will be measured, along with height, weight, and waist circumference.
- Concomitant medication information will be documented.
- If a female is of childbearing potential, the use of effective contraception will be discussed (see [Attachment 4](#)).
- Study diaries will be collected and the following reviewed:
 - Self-monitoring of blood glucose results
 - Hypoglycemia events
 - Adverse event information
 - The date and time of all study drug injections
 - Females: The date of the last menstrual period
- The patient will receive:
 - Study diaries
 - Glucometer supplies
 - Diet and exercise instruction for their T2DM
 - Study drug
- The visit will conclude with another collection of blood for PK (this post dose PK level must be drawn at least 1 hour and up to 12 hours after study drug injection) noting the exact date and time and the elapsed time since study drug injection.*

The patient will be sent home with appointments for 2 telephone visits, which will occur in 5 and 9 weeks (Weeks 18 and 22), and a clinic visit in 13 weeks (Week 26) in the fasted state for the final double-blind visit.

*All other laboratories required to be collected at this visit (including ADAs) may be collected with either the first or the second blood draw. In females of childbearing potential, the laboratories will include a serum pregnancy test (a local urine pregnancy test must also be performed).

Weeks 18 and 22: Telephone Visits (Visit Window up to ± 7 days)

At these visits, the following will be performed:

- Concomitant medication will be documented.
- If a female is of childbearing potential, the use of effective contraception will be discussed (see [Attachment 4](#)).
- The contents of the study diaries for the previous month will be reviewed:
 - Self-monitoring of blood glucose results
 - Hypoglycemia events
 - Adverse event information
 - The date and time of all study drug injections
 - Females: The date of the last menstrual period

Week 26: Final Double-Blind Visit (Visit Window up to ± 6 days)

At the final visit for the double-blind portion of the trial, patients will return to the clinic in the morning in the fasted state. This visit must occur on the date of the patient's usual weekly injection of study drug and before the patient has injected study drug, as blood will be collected for a pre-dose PK level prior to study drug injection.

The following will be performed:

- A physician will perform a physical exam and Tanner staging.
- Vital signs will be measured, along with height, weight, and waist circumference.
- Concomitant medication information will be documented.
- If a female is of childbearing potential, the use of effective contraception will be discussed (see [Attachment 4](#)).
- Study diaries will be collected and the following reviewed:
 - Self-monitoring of blood glucose results
 - Hypoglycemia events
 - Adverse event information
 - The date and time of all study drug injections
 - Females: The date of the last menstrual period
- As this is the end of the double-blind period, the dose of background diabetes medication (i.e., metformin and basal insulin) may be re-adjusted as needed.
- Blood for PK (pre dose) and other scheduled laboratories will be collected and sent to the central laboratory.
 - A local urine pregnancy test and a serum pregnancy test must be performed for all females of childbearing potential.
- An electrocardiogram (ECG) will be performed.
- The patient will complete the EQ-5D-Y health outcomes questionnaire.

- The patient will receive:
 - Study diaries
 - Glucometer supplies
 - Diet and exercise instruction for their T2DM
- After the site processes the visit in the IWRS, patients will be dispensed the appropriate open-label study drug.
- As it is the patient's dosing day, at the conclusion of this visit, if desired, the patient's first dose of open-label study drug may be administered.

The patient will be sent home with appointments for 3 telephone visits, which will occur in 1 week (Week 27), 5 weeks (Week 31), and 9 weeks (Week 35), and with a clinic visit in 13 weeks (Week 39) in which the patient should return in the non-fasted state.

Open-label period:

This treatment period will last for 26 weeks. With the exception of a telephone visit scheduled 1 week after the open-label period begins, study visits will occur approximately monthly: face-to-face visits in the clinic will occur approximately every 3 months (Week 39 and Week 52) and telephone visits will occur in between the face-to-face visits (Weeks 31, 35, 44, and 48).

If pregnancy is suspected at any time in females of childbearing potential, a local urine pregnancy test will be performed and a serum pregnancy test will be sent to the central laboratory. If the patient is pregnant, she must be permanently discontinued from study drug and the study.

Weeks 27, 31, and 35: Telephone Visits (Visit Window up to ± 7 days [+7 days for Week 27])

At these visits, the following will be performed:

- Concomitant medication will be documented.
- If a female is of childbearing potential, the use of effective contraception will be discussed (see [Attachment 4](#)).
- The contents of the study diaries for the previous month will be reviewed:
 - Self-monitoring of blood glucose results
 - Hypoglycemia events
 - Adverse event information
 - The date and time of all study drug injections (Note: Date and time of first dose of open-label study drug, which should be administered after the Week 26 visit [Visit 9] is completed, will be recorded on the exposure form at the Week 27 visit [Visit 10])
 - Females: The date of the last menstrual period

Week 39: Clinic Visit (Visit Window up to ± 7 days)

At the half-way point in the open-label portion of the clinical trial, the patient will return to the clinic in the non-fasted state on their usual dosing day or up to 2 days later. The following will be performed:

- If it is the patient's dosing day, and the patient has not yet taken their weekly dose, the patient's study drug will be administered.
- A symptom-directed physical exam by a physician will be performed.
- Vital signs will be measured, along with height and weight.
- Concomitant medication information will be documented.
- If a female is of childbearing potential, the use of effective contraception will be discussed (see [Attachment 4](#)).
- Study diaries will be collected and the following reviewed:
 - Self-monitoring of blood glucose results
 - Hypoglycemia events
 - Adverse event information
 - The date and time of all study drug injections
 - Females: The date of the last menstrual period
- Blood will be collected and sent to the central laboratory. If it is the patient's dosing day, the blood may be collected any time after the patient's dose has been administered.
 - Collection of blood for PK taken any time up to 2 days post dose
 - A local urine pregnancy test and a serum pregnancy test must be performed for all females of childbearing potential.
- The patient will receive:
 - Study diaries
 - Glucometer supplies
 - Diet and exercise instruction for their T2DM
 - A supply of study drug.

The patient will be sent home with appointments for 2 telephone visits, which will occur in 5 weeks (Week 44) and 9 weeks (Week 48), and a clinic visit in 13 weeks (Week 52) in the fasted state for the final open-label visit.

Weeks 44 and 48: Telephone Visits (Visit Window up to ± 7 days)

At these visits, the following will be performed:

- Concomitant medication will be documented.
- If a female is of childbearing potential, the use of effective contraception will be discussed (see [Attachment 4](#)).
- The contents of the study diaries for the previous month will be reviewed:
 - Self-monitoring of blood glucose results
 - Hypoglycemia events
 - Adverse event information
 - The date and time of all study drug injections
 - Females: The date of the last menstrual period

Week 52: Final Open-label Visit (Visit Window up to ± 7 days)

At the final visit for the open-label portion of the trial, patients will return to the clinic in the morning in the fasted state. The following will be performed:

- A physician will perform a physical exam (and Tanner staging, if appropriate).
- Vital signs will be measured, along with height and weight.
- Concomitant medication information will be documented.
- If a female is of childbearing potential, the use of effective contraception will be discussed (see [Attachment 4](#)).
- Study diaries will be collected and the following reviewed:
 - Self-monitoring of blood glucose results
 - Hypoglycemia events
 - Adverse event information
 - The date and time of all study drug injections
 - Females: The date of the last menstrual period
- Blood and urine will be collected and sent to the central laboratory.
 - Collection of blood for PK any time during this visit
 - A local urine pregnancy test and a serum pregnancy test must be performed for all females of childbearing potential.
- The patient will complete the EQ-5D-Y health outcomes questionnaire.
- An ECG will be performed.
- The patient will receive:
 - Study diaries
 - Glucometer supplies
 - Diet and exercise instruction for their T2DM
- As this is the end of the open-label period and the patient will stop taking dulaglutide, the patient's background diabetes medication must be adjusted.
 - Glucagon-like peptide-1 receptor agonists (including, but not limited to, exenatide, liraglutide, albiglutide, and lixisenatide) and dipeptidyl peptidase-IV (DPP-IV) inhibitors (including, but not limited to, sitagliptin, vildagliptin, saxagliptin, linagliptin, anagliptin, teneligliptin, and alogliptin) are not allowed during the next 30 days.

The patient will be sent home with an appointment for a final visit, which will occur in 30 days in the non-fasted state (safety follow-up visit; Visit 801).

Safety follow-up period: Approximately 30 days after completion of the 26 weeks of open-label treatment, patients will return in the non-fasted state to complete a safety follow-up visit (Visit 801).

Week 56: Safety Follow-Up Visit (Visit Window up to ±7 days)

The patient will return to the clinic in the non-fasted state. At this visit, the following will be performed.

- Vital signs will be measured, along with height and weight.
- Concomitant medication information will be documented.
- Blood will be drawn and sent to the central laboratory.
 - Collection of blood for PK any time during this visit.
- Study diaries and their contents will be collected:

- Adverse event information
- Females: The date of the last menstrual period
- Patients must return any remaining study equipment to the investigative site.

Patients discontinuing the study early should have this visit approximately 30 days after the early termination visit. Patients who discontinue the study before randomization do not need to complete this visit.

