10.3. Pharmacokinetics and Pharmacodynamics

Pharmacokinetics: For population PK (PopPK) and exposure-response analyses, 6 blood samples will be collected from all patients (see [Attachment 1](#)).

Together with the 3 additional PK samples to be collected from each patient in the PK/PD addendum, these PK samples will provide information for PopPK and exposure-response modeling purposes, as well as be utilized for the interpretation of immunogenicity data and whether it has any impact on dulaglutide PK. Collectively, PK sample size and sampling times in the main protocol and PK addendum have been optimized using a standard PK optimal sampling approach.

Pharmacodynamics: Additionally, blood for fasting insulin, C-peptide, glucose, and adiponectin will be taken to assess the effect of dulaglutide on insulin resistance, beta cell function, and adiponectin.

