- o Includes both pre- and postdose blood draws. At Week 13 (Visit 6), one PK sample is to be taken predose and then study drug should be administered. Later in the visit, one PK sample should be taken between 1 to 12 hours after administration of the Week13 dose. At Week 26 (Visit 9), the PK sample is to be taken predose. At Week 39 (Visit 13), the PK sample can be taken up to 2 days postdose. At Week 52 (Visit 16), the PK sample can be taken at any time during the visit. At Week 56 (Visit 801) and early discontinuation, the sample can be taken at any time during the visit.
- p When a PK sample is drawn, an ADA sample should also be drawn at the same time or within 30 minutes of the PK sample (see footnote n), with the exception of the randomization visit, where an ADA sample is drawn but not a PK sample.

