Attachment 5. Protocol GBGC IDF-ISPAD Criteria for the Diagnosis of Diabetes

Criteria for the diagnosis of diabetes mellitus^a

1. Symptoms of diabetes plus casual plasma glucose concentration ≥ 11.1 mmol/L (200 mg/dL)^a.
Casual is defined as any time of day without regard to time since last meal.

or

2. Fasting plasma glucose ≥ 7.0 mmol/L (≥ 126 mg/dL)^b.
Fasting is defined as no caloric intake for at least 8 hours.

or

3. 2-hour postload glucose ≥ 11.1 mmol/L (≥ 200 mg/dL) during an oral glucose tolerance test (OGTT).

The test should be performed as described by World Health Organization, using a glucose load containing the equivalent of 75 g anhydrous glucose dissolved in water or 1.75 g/kg of body weight to a maximum of 75 g (2).

4. HbA1c ≥ 6.5 .

However, there are difficulties with assay standardization and individual variation in the relationship between blood glucose and HbA1c, which may outweigh the convenience of this test.

^a Corresponding values are ≥ 10.0 mmol/L for venous whole blood and ≥ 11.1 mmol/L for capillary whole blood.

^b Corresponding value is ≥ 6.3 mmol/L for both venous and capillary whole blood.

Reference: IDF [WWW]

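### The Week 13 footnote lets tests designated as fasting be drawn 1 to 12 hours after dosing, with no instruction to stay fasted, and so conflicts with their fasting designation

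*Protocol*

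**What the plan says.** Protocol 7.1 (Week 13 clinic visit) sets this order of events.

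- On arrival: "the patient will return to the clinic in the fasted state".
- First draw: "Blood will be collected for a predose PK level, noting the exact date and time". The injection follows.
- Second draw, at the end of the visit: "this post dose PK level must be drawn at least 1 hour and up to 12 hours after study drug injection". Footnote o of the Study Schedule (Attachment 1) agrees: "Later in the visit, one PK sample should be taken between 1 to 12 hours after administration of the Week13 dose".
- Everything else: "All other laboratories required to be collected at this visit (including ADAs) may be collected with either the first or the second blood draw".

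The Study Schedule lists fasting glucose, fasting insulin, fasting C-peptide, fasting adiponectin and the standard chemistry panel at Week 13. Protocol 10.3 gives the purpose: "blood for fasting insulin, C-peptide, glucose, and adiponectin will be taken to assess the effect of dulaglutide on insulin resistance". Attachment 2 also labels insulin, C-peptide and adiponectin as fasting, and lists glucose in both fasting and random forms. Lipids carry no fasting label there.

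The only definition of fasting is in Attachment 5, among the diagnostic criteria: "Fasting is defined as no caloric intake for at least 8 hours".

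**The concern.** A site that draws every Week 13 tube except the predose PK sample several hours after injection, once the patient has eaten, is within the footnote but has not delivered fasting samples. The protocol does not say which text governs.

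Two uses of the data are exposed. First, Weeks 13 and 26 are the only postbaseline points for the exploratory objective on insulin resistance, beta-cell function and adiponectin (Protocol 6.3). SAP 5.16.6 derives HOMA2, the reciprocal of fasting insulin or C-peptide, and an insulin sensitivity score from these visits and models them together, so a shift in meal state at one visit could be read as a change over time. Second, Week 13 FBG is the one intermediate value feeding the analysis of Week 26 FBG, a key secondary endpoint.

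**Working it through.** The plan states no figure to reproduce here. The check sets the texts side by side, with a little arithmetic on timing.

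**Step 1. Sampling conditions by visit (Protocol 7.1, Attachment 1).**

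| Visit | State on arrival | Fasting tests relative to dose |
|---|---|---|
| Week 0 | fasted | before; injection comes at the end of the visit |
| Week 13 | fasted | before, or 1 to 12 hours after |
| Week 26 | fasted, morning | before |

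Week 13 is the only one of the three where a fasting test may follow the injection.

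**Step 2. Length of fast needed.** Assume that the 8-hour definition in Attachment 5 also governs visits, that the patient arrives with exactly that fast, and that the injection is prompt.

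- Earliest second draw: 8 + 1 = 9 hours without food.
- Latest second draw: 8 + 12 = 20 hours without food.

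The early end is feasible. The late end is unlikely without an instruction, and there is none.

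**Step 3. Does another rule close the gap?** Footnote m of the Study Schedule ties serum hormones to a morning fasting draw. Insulin, C-peptide and adiponectin have no such footnote. Neither the protocol nor the SAP requires fasting status to be recorded at each draw, and the SAP has no rule for Week 13 samples taken after the dose.

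**Step 4. Where the Week 13 values go.**

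- *Exploratory biomarkers (SAP 5.16.6).* Used directly: one of two postbaseline points. Triglycerides enter the log insulin sensitivity score with coefficient −0.00235 per mg/dL. Each 10 mg/dL rise therefore changes the log score by 10 × (−0.00235) = −0.0235, a factor of exp(−0.0235) = 0.977. The documents do not say how far a meal would raise triglycerides here.
- *FBG, efficacy estimand (SAP 5.12.1).* Week 13 enters the repeated-measures model. It acts on the Week 26 estimate indirectly, mainly for patients whose Week 26 value is missing or censored after rescue.
- *FBG, treatment regimen estimand (SAP 5.11.3, applied by 5.12.1).* Missing dulaglutide values are imputed without intermediate data. Missing placebo values are imputed with it. Week 13 FBG can enter only through the placebo arm.
- *HbA1c.* Not specified as a fasting test, so not affected.

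**Step 5. Could the error differ by arm?** The choice of draw is made under blinding, so there is no reason for late draws to cluster in one arm. The response to a meal could still differ: Protocol 5 describes effects of this drug class on glucose-dependent insulin secretion, and on postprandial glucose with one short-acting member. This is a possibility, not a quantity.

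**The case against.** The strongest reply is that the footnote settles which draw may carry the tubes and does not waive fasting. The visit is a fasting visit, the tests are named as fasting, and a site that follows both texts will keep the patient fasted or use the first draw. The second draw belongs to the same visit and may come only an hour after the injection. This stands in part: a reader might infer that Week 13 values are simply non-fasting, and the documents do not support that. What survives is that a specific permission sits beside a general label with nothing to reconcile them.

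Three further inferences are tempting and should not be drawn.

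- *That antibody testing is compromised by a postdose draw.* Anti-drug antibodies (ADA) are not a fasting test. Protocol 10.5.2 and footnote p pair ADA with PK samples by design, including postdose ones at later visits, and neither document discusses drug interference in the assay.
- *That the resistance index would be inflated by a stated multiple.* The documents give no meal responses for glucose or insulin. SAP 5.16.6 also chooses HOMA2 over the original equations, so multiplying assumed rises would not describe the planned endpoint.
- *That the FBG hypotheses are undermined.* They are tested at Week 26, where sampling is fasted and predose. The route from Week 13 is indirect.

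It is also fair that lipids are not labelled fasting, so the triglyceride point is only a possible extension.

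**Conclusion.** The point holds as an unreconciled conflict: the Week 13 footnote permits a draw that does not secure the fasting state the same protocol requires for glucose, insulin, C-peptide and adiponectin. The main reach is one of the two postbaseline points of an exploratory objective. There may be a smaller, indirect effect on Week 26 FBG. The documents do not say how many samples were drawn after the dose or how many of those were fed, so neither effect can be sized. The 9 to 20 hour range rests on carrying the diagnostic 8-hour definition over to visits. The primary endpoint is not affected. The change is worth making because the permission can yield worse data and removing it costs almost nothing.

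**What to change.** **Protocol.** Amend the Week 13 footnote so that fasting glucose, insulin, C-peptide and adiponectin, and preferably the lipids used in the insulin sensitivity score, must be collected with the first (predose, fasted) draw. Other tests, including ADA, may stay with either draw. The cost is a slightly larger first draw at the same visit.

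**SAP, for samples already taken.** Use the recorded draw and injection times to identify Week 13 fasting tests taken after the dose. Before unblinding, prespecify a sensitivity analysis that leaves out those not known to be fasted. Do not drop all postdose samples from the main analysis: one taken about an hour after injection may be validly fasted. Protocol 10.5.3 describes the draw-time record for PK samples, so confirm that it also identifies the draw used for the other tubes. The cost is one additional analysis.

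**Timing.** The SAP part probably carries most of the value. The last patient visit is estimated for January 2022. If that is Week 56, the last Week 13 visit falls 56 − 13 = 43 weeks earlier, in March or early April 2021, and the SAP was approved on 18 February 2021. An amended footnote would therefore reach few patients on those estimates.
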